#### **Neurovalens Limited**

Identifier: EXP18020 Clinical Study Identifier: 243973

Lastly the blinding of subjects will be assessed by comparing the subject provided responses of which treatment device they think they have been assigned to, compared to what treatment device they actually received.

#### 5. SAMPLE SIZE CONSIDERATIONS

The primary outcomes are percent total body weight loss from the start of treatment (as a percentage of baseline total body weight), and the proportion of subjects who lose at least 5% of their baseline total body weight. These outcomes will be assessed at the 6-month mark.

Power calculations are based on simulation (for full details see supporting documents EXP18006 Simulation Plan v4.1 and EXP18006 Simulation Report v1.0). Simulation assumptions were informed by pilot data and data from the Modius device as follows:

- 90Kg median baseline weight in both groups (log-normal distribution with CV=24%),
- 6.6% mean percent weight loss in the active group at 6 months (SD 3.9%),
- 3.1% mean percent weight loss in the control group at 6 months (SD 3.9%),
- correlation between baseline weight and weight loss at 6 months of 0.4.

Under these assumptions, with a sample size of 180 participants randomized 1:1 active: placebo, there is greater than 80% power to demonstrate both the weight loss mean and categorical acceptance criteria at the 6 month time point.

Under an assumption of no difference between active and control but the same assumptions around SDs and correlations there is <2% probability overall of a type-I error with this sample-size.

Anticipating a drop-out rate of 10%, we will plan to recruit n = 200 total subjects overall in the study across all sites.

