	$\mu A$ and $\mu C$ are the underlying population mean percentage weight loss on active and control respectively
	This single study efficacy acceptance criterion for the EU regulatory clearance pathway will be treated to the same statistical analysis as the mean criterion for the USA regulatory clearance pathway.
Rationale for Number of Subjects	The primary outcomes are TBWL from the start of treatment (as a percentage of baseline total body weight), and the proportion of subjects who lose at least 5% of their baseline total body weight. These outcomes will be assessed at 6-months.
	
 
Power calculations are based on simulation with assumptions informed by pilot data and the Modius weight-loss device as follows:
 
90kg median baseline weight in both groups (log-normal distribution with CV=24%)
 
6.6% mean percent weight loss in the active group at 6 months (SD 3.9%),
 

Vestibular Stimulation to Trigger Adipose Loss (VeSTAL) Clinical Trial			21 of 112
Clinical Protocol for VeSTAL			
243973(NI)_181094(UCSI USA)	11 Pavision Number		
Study Reference Number	Document Type	Document Number	Revision Number

	
 
3.1% mean percent weight loss in the control group at 6 months (SD 3.9%),
 
correlation between baseline weight and weight loss at 6 months of -0.4.
 
	
	Under these assumptions, with a sample size of 180 participants randomized 1:1 active: placebo, there is greater than 80% power to demonstrate both the weight loss mean and categorical acceptance criteria at the 6 month timepoint.	

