## Study Acceptance Criteria USA:

- Mean: There should be at least a 2% total body weight loss (TBWL) superiority margin between the active-product and sham-treated groups.
- Categorical: The proportion of participants who lose 5% TBWL or more in the active-product group is at least 50%, independent of the sham control

Both weight loss efficacy acceptance criteria must be met to claim success. These criteria can be specified in mathematical formulae as follows:

Rejection of both the null hypotheses  $\mu A - \mu C \le 2\%$  and  $\pi A \le 50\%$  at the 2.5% (1-sided) level Where:

 $\mu$ A and  $\mu$ C are the underlying population mean percentage weight loss on active and control respectively

 $\pi A$  is the underlying population proportion of subjects who lose  $\geq 5\%$  of baseline body weight on active.

Vestibular Stimulation to Trigger Adip Clinical Trial Project Name	68 of 112		
Clinical Protocol for VeS			
243973(NI)_181094(UCSD USA)	11		
Study Reference Number	Document Type	Document Number	Revision Number

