### Power Calculation

The statistical plan was developed in conjunction with the biostatistics and trial design optimization company Exploristics (https://exploristics.com). Multiple simulation scenarios (each with 1000 iterations) were conducted in their KerusCloud platform to determine an appropriate study size for this evaluation. KerusCloud is a cloud-based, virtual simulation environment for optimizing clinical study design and analysis.

The primary outcomes are mean TBWL from the start of treatment (as a percentage of baseline total body weight), and the proportion of subjects who lose at least 5% of their baseline total body weight. These outcomes will be assessed at the 6-month timepoint.

Power calculations are based on simulation with assumptions informed by pilot data and the Modius weightloss device as follows:

90kg median baseline weight in both groups (log-normal distribution with CV=24%)

6.6% mean percent weight loss in the active group at 6 months (SD 3.9%),

3.1% mean percent weight loss in the control group at 6 months (SD 3.9%),

correlations between baseline weight and weight loss at 6 months of -0.4.

Under these assumptions, with a sample size of 180 participants randomized 1:1 active: placebo, there is a greater than 80% power to demonstrate both the mean and categorical weight loss acceptance criteria at the 6-month timepoint.

Under an assumption of no difference between active and control but the same assumptions around SDs and correlations there is  $\leq 2\%$  probability of a type-I error with this sample-size.

Vestibular Stimulation to Trigger Adip Clinical Trial Project Name	99 of 112		
Clinical Protocol for VeSTAL			
Document Title			
243973(NI)_181094(UCSD USA)	11		
Study Reference Number	Document Type	Document Number	Revision Number

Anticipating a drop out rate of 10%, we will plan to recruit n = 200 total subjects overall in the study across both sites.

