# Neurovalens Limited Identifier: EXP18020

Clinical Study Identifier: 243973

For the purpose of the *EU regulatory clearance pathway*, the study will be deemed to have met the efficacy criteria if the hypothesis is rejected, and the following numerical criterion is achieved:

• The difference between the mean percentage weight loss of participants using the VeSTAL device and the sham control is at least 2% as observed from the mean estimates.

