## 12.1.1 Primary Efficacy Analyses

As the primary efficacy endpoints differ between regulatory clearance pathways, the primary efficacy analyses also differ accordingly.

For both the *EU and USA regulatory clearance pathways*, the primary efficacy endpoint will be summarized using summary statistics for the percentage weight loss at the 6 month time point. The mean percentage weight loss will also be presented graphically, by treatment group, over time. Summaries and graphical outputs will be produced for observed data unless specified otherwise..

For the continuous efficacy endpoint, mean percentage weight loss at 6 months, the difference between treatment groups will be assessed using a linear model controlling for covariates of interest: gender and baseline weight. The least square (LS) mean difference between groups will be assessed for a statistically significantly difference from 0 i.e. p-value <0.05. For the USA regulatory clearance pathway, the lower limit of the confidence interval of the LS Mean difference between groups will be assessed against the 2% target for a successful study, whereas the EU regulatory clearance pathway will assess whether the LS mean difference between groups is significantly different from zero. Analysis using multiple imputation for missing data will be primary, with the LOCF and BOCF imputation methods used for supportive analyses.

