### 12.1.2 Supportive Primary Efficacy Analyses

For the purposes of the *USA regulatory clearance pathway*, the number and percentage of people achieving a loss of at least 5% of their body weight by the 6 month time point in the VeSTAL device treatment group will be presented with a two-sided 95% exact binomial confidence interval for the response rate. The criterion for success is that the lower bound of the 95% confidence interval of the response rate in the VeSTAL device group exceeds 50%. The analysis will use the multiple imputation for missing data as primary, with the LOCF and BOCF imputation methods as supportive.

A Fisher's exact test will also be used to compare the response rates in each treatment group and to detect whether the difference between groups is statistically significant. This will be repeated using multiple imputation, LOCF and BOCF methods for missing data. For the multiple imputation-based analysis, the median p-value approach will be used to generate the Fisher's exact test p-value (Eekhout 2017) and the exact confidence intervals described above will be produced using the imputation with a p-value equal to or nearest the median p-value.

In addition, a sensitivity analysis will be performed with the binary weight loss endpoint, to assess the impact of imputing the best and worst case scenarios for the binary response, when the total body weight loss at 6 months is missing. As per section 10.2, a tipping point analysis will also be utilised to demonstrate the level of imputation which changes the significance of the binary weight loss criterion.

No supportive primary efficacy analyses are required for the *EU regulatory clearance pathway*.

Identifier: EXP18020 Clinical Study Identifier: 243973

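### The stated power of more than 80% to meet both US criteria does not follow from the plan's own inputs; with 180 evaluable subjects it is about 72-73%

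*SAP*

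**What the plan says.** The power statement appears three times: in SAP section 5 ("greater than 80% power to demonstrate both the weight loss mean and categorical acceptance criteria"), in the protocol synopsis under the rationale for the number of subjects ("greater than 80% power to demonstrate both the weight loss mean and categorical acceptance criteria at the 6 month timepoint"), and in the protocol's Power Calculation in section 34 ("greater than 80% power to demonstrate both the mean and categorical weight loss acceptance criteria"). Each gives 180 participants randomized 1:1 and the same means, SD and baseline weight distribution. Ten percent dropout then gives 200 randomized. The protocol describes the method as "Multiple simulation scenarios (each with 1000 iterations"); the simulation plan and report are cited in the SAP but are not part of the documents.

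Only the US pathway has a categorical criterion, so the statement can only refer to US success. Protocol section 18.1 says "Both weight loss efficacy acceptance criteria must be met to claim success", and defines this as rejecting both a mean difference of 2% or less and an active response rate of 50% or less, each at one-sided 2.5%. The SAP applies the rule as follows:

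- Mean (section 12.1.1): "the lower limit of the confidence interval of the LS Mean difference between groups will be assessed against the 2% target", from a linear model with gender and baseline weight.
- Responders (section 12.1.2): the "lower bound of the 95% confidence interval of the response rate in the VeSTAL device group exceeds 50" percent, using the exact binomial interval.

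The EU rule is weaker. It needs a significant difference from zero and an observed difference that "is at least 2% as observed from the mean estimates" (SAP section 2.3.1).

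**The concern.** The assumed difference is 3.5 points, but the US mean criterion tests against a margin of 2, so only 1.5 points of signal remain, against an SD of 3.9 with 90 per arm. That puts the mean test alone near 80%. Requiring a second criterion as well can only lower the figure, so a joint power above 80% looks impossible on these inputs.

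The statement is the justification for 180 evaluable and 200 randomized subjects. If it is wrong, the trial has a materially larger chance of failing the US rule under the sponsor's own assumptions than the plan says, and a reader interpreting a missed US criterion would be misled about how likely that was. The tests, thresholds and type I error are not affected.

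**Working it through.** **Inputs** (SAP section 5 and protocol Power Calculation): mean loss 6.6% active and 3.1% control; SD 3.9% in both arms; log-normal baseline weight with median 90 kg and CV 24%; correlation of baseline weight with weight loss 0.4 in the SAP and -0.4 in the protocol (both signs were run); 90 per arm. Percentage loss is taken as normal, and adjustment is for baseline weight only, because the documents state neither another distribution nor a gender effect.

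**Sample size arithmetic.** 180 / 0.9 = 200, as stated.

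**Mean criterion alone.**
- Signal above the margin: (6.6 - 3.1) - 2 = 1.5.
- Adjusted SE = 3.9 × sqrt(1 - 0.4²) × sqrt(2/90) = 0.533, and 1.5/0.533 = 2.81. Power is 79.95% by noncentral t (80.4% by normal approximation).
- Unadjusted SE = 3.9 × sqrt(2/90) = 0.581. Power is 72.8%.

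**Responder criterion alone.**
- Active response rate = Φ((6.6 - 5)/3.9) = Φ(0.410) = 65.9%.
- The exact lower limit exceeds 50% with at least 55 of 90 responders (one-sided error 0.0223 at a true rate of 50%). Power is 85.8%.

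**Bounds on the joint power.** It cannot exceed 79.95%, the smaller of the two. If the criteria were independent it would be 0.7995 × 0.858 = 0.686. They share the active-arm data and are positively related, so the true value lies between these figures.

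**Joint power by simulation** (60,000 trials per case, analysis of covariance on baseline weight with t-based 95% limits, both criteria required):

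| Correlation | 90/arm, adjusted | 90/arm, unadjusted | 100/arm, adjusted | 100/arm, unadjusted |
|---|---|---|---|---|
| -0.4, log weight | 72.1% | 67.0% | 76.3% | 71.8% |
| +0.4, log weight | 72.5% | 67.7% | 76.3% | 71.8% |
| -0.4, raw weight | 73.2% | 68.2% | 77.0% | 72.1% |
| +0.4, raw weight | 71.7% | 66.8% | 76.2% | 71.6% |

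A second run with 40,000 trials per case gave 71.6% to 73.3% for the adjusted analysis at 90 per arm.

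**Could it be simulation noise?** With 1000 iterations the Monte Carlo SE is sqrt(0.725 × 0.275/1000) = 0.014. The gap to 80% is 7 to 8 points, about 5 SE.

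**Which rules do give 80% or more at 90 per arm?**
- EU-type mean rule plus the exact responder rule: about 85-87%.
- Both US tests at one-sided 5%: about 81-82%.
- Each US criterion read separately: about 80% and 86%.
- EU mean rule alone: 99.7%.

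None of these is the US joint rule.

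**What would deliver 80% jointly?**
- Sample size (50,000 trials per case): 104 per arm gives 79.1%, 106 gives 80.2%, 107 gives 79.6% and 108 gives 81.4%. The dip at 107 reflects the discrete exact test. About 212 to 216 evaluable are needed; 212/0.9 is about 236 randomized and 216/0.9 = 240.
- Alternatively, at 90 per arm, the baseline covariates would have to explain about 40% of the variance (35% gives 78.7%, 40% gives 79.9%, 45% gives 81.2%). The stated correlation gives 0.4² = 16%.

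**The case against.** The arithmetic for the US rule is not in dispute, but four points can be made against the size or importance of the finding.

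- **Covariates.** The protocol's model in section 34.1 also lists age and study site, and the documents do not say which covariates the simulation used. If further covariates explained an extra 5% or 10% of variance, joint power would be 74.1% or 75.8%; it reaches 79.8% only at an extra 24%. So 72-73% is a baseline-weight-only figure, and that should be stated. The gap does not close, and SAP section 13 says its analyses supersede the protocol's, which leaves gender as the only other covariate.
- **Normality.** The 65.9% response rate, and hence the exact joint value, depend on percentage loss being normal. This stands as a caveat. The cap of about 80% from the mean test hardly depends on it.
- **Looser reading of the responder criterion.** The acceptance bullets can be read as an observed proportion of at least 50%. With the US mean rule that gives 79.7%, within noise of 80%. The formal null hypotheses in the protocol and the confidence-limit rule in the SAP override this reading, though it could be another origin of the figure.
- **Timing.** SAP version 1.2 was written just before database lock, so the power figure no longer drives enrolment and cannot change the result. That limits the consequence to the statement itself and to how a failed criterion is read. The statement remains wrong as written.

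**Conclusion.** The concern holds. On the listed inputs and the stated US rule, joint power with 180 evaluable subjects is about 72-73% with baseline adjustment (71.7% to 73.2% over both correlation signs and both weight scales) and about 67-68% without. With all 200 observed it is 76-77% adjusted and about 72% unadjusted. These values assume normal percentage loss and adjustment for baseline weight only.

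The firmer part of the conclusion needs no joint simulation: the mean test alone has about 80% power, so a joint figure above 80% is not available on these inputs. Where the stated figure came from cannot be settled without the simulation report. An EU-type mean rule, tests at one-sided 5%, or criteria powered separately would each produce something like it.

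**What to change.** 1. Check the figure against the simulation report cited in SAP section 5, and state in the SAP which mean rule, which covariates and which distribution were simulated.
2. Unless that report shows different inputs or a different rule, restate joint US power as about 72-73% with 180 evaluable subjects (76-77% if all 200 are observed), with the normality and baseline-weight-only assumptions written beside it. Make the same change in SAP section 5, the protocol synopsis and the protocol Power Calculation.
3. Give EU power separately (above 99%).

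Two clarifications are optional. The sign of the correlation differs between the documents (possibly a text-extraction artefact) and could be confirmed; it moves power by less than 2 points. The type I figure of about 2% is true at its stated condition of no difference, but the SAP could add that the US rule's maximum error is the nominal 2.5% at a true difference of 2% (2.2% at a true response rate of 50%).

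The cost is wording in three places and a less favourable stated US power. No change to enrolment, tests, thresholds or alpha is asked for.

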## 6. DATA MANAGEMENT

## **6.1 Data Collection and Preparation**

The daily use of the device at home will be recorded automatically via the device application. Weight and body fat measurements will be recorded by study personnel at each site, who will enter data from source documents into the protocol-specific Case Report Form (CRF). All subject data will be transcribed from the subject level CRF and saved in excel format. For the purposes of the final analysis, the clinical study database will be cleaned, with particular attention given to the critical data and locked to prevent any further data entry or adjustment prior to the study reporting of 6 month data. Further details of the data management process are provided in the study Data Collection and Management SOP (Data Collection and Management for Vestibular Stimulation to Trigger Adipose Loss (VeSTAL) Clinical Trial (Study References 243973 and 181094), Ref NVDC020119, Revision 2).

Identifier: EXP18020 Clinical Study Identifier: 243973

## **6.2 Unblinding of Data**

The clean, locked, blinded data will be transferred to the lead statistician in password protected excel files, one per site, via Exploristics's file sharing server. Likewise, the randomization list, in the form of a password protected excel file, will be requested from Neurovalens's randomization representative and shared with the lead statistician via Exploristics's file sharing server. Passwords for both documents will be shared separately via phone, to protect the security of the data.

The statistician, supported by a lead programmer, will import the data from Exploristics's secure server into SAS® and merge with the randomization list to unblind the data, such that it can be made analysis ready.

## 7. ANALYSIS POPULATIONS

The efficacy analyses will be performed on the Intention to Treat (ITT) population, which will include all randomized subjects. Subjects in the ITT Population will be classified according to the treatment as randomized.

Similarly, the safety and tolerability analyses will be performed on the Safety Analysis Set (SAS) population, which will include all randomized subjects who received either the VeSTAL or sham control devices (i.e., recorded at least one session of use defined as usage on at least one day).

However, subjects in the Safety Analysis Set will be classified according to the treatment received, which may on occasions differ from that randomized.

Should any major protocol deviations occur on study, the Per Protocol (PP) population will be defined which excludes any subjects who violate the protocol in terms of a major deviation. Of particular attention will be those subjects who are non-compliant with device usage. For example, to be included in the PP population, subjects must use the device for at least an average of three and a half hours a week for at least four of the first 6 months. If the PP population contains less than 95% of the ITT population then efficacy analyses will be repeated on the PP population.

#### 8. TREATMENT COMPARISONS

All treatment comparisons will be performed between the VeSTAL and the sham control devices' treatment groups. Statistical comparisons will be performed under the hypothesis of no significant difference between groups, unless otherwise specified. The level of significance for the primary efficacy endpoints will not be adjusted for multiple testing as detailed in section 9.4. However, as the endpoints VAT loss, LDL, fat loss, lean muscle mass, atherogenic index, systemic inflammation, calorie intake and quality of life will be analyzed with the intention of making labeling claims, the level of significance for each endpoint will be adjusted for sequential testing (detailed in section 9.4). All remaining statistical comparisons, including the secondary efficacy endpoints will declare a significant difference between groups at the 5% significance level.

### 9. GENERAL CONSIDERATIONS FOR DATA ANALYSES

In general, continuous data will be summarized by the number of subjects in the analysis population (N), mean, standard deviation, minimum, median and maximum. The mean and median will be presented to one more decimal place than the original data, the minimum and maximum to the same

#### **Neurovalens Limited**

Identifier: EXP18020

Clinical Study Identifier: 243973

number of decimal places as the original data and the standard deviation presented to two more decimal places than the original data.

In summaries of categorical data, frequencies and percentages will be used. Subjects with missing values will be summarized in a 'Missing' category. Generally, percentage will be displayed to one decimal place and based on the number of subjects in the analysis population.

For statistical comparisons, p-values will be presented to 3 decimal places with p-values less than 0.001 will be presented as <0.001 in Tables, Figures and Listings (TFLs). Unless otherwise specified, confidence intervals will be two-sided with 95% confidence limits, and presented to the same number of decimal places as the point estimate.

If the assumptions for any planned linear model are not achieved, then a non-linear model such as one including quadratic terms will be investigated. If, after this, a satisfactory model still cannot be found then non-parametric methods will be applied.

All analyses will be performed using SAS® v 9.4 (or higher).

